4.2 STUDY ENDPOINTS

4.2.1 PRIMARY ENDPOINT

1. Complete response (CR) to the therapeutic intervention
2. Time to response to CLL to the therapeutic intervention

4.2.2 SECONDARY ENDPOINTS

1. Overall response rate (ORR) [CR + PR]
2. Restoration of immune response as measured by:

- a. Decreased markers of T-cell exhaustion
- b. Increased of quantitative immunoglobulin levels and subtype
- 2. Safety and toxicity of the combination
- 3. Progression free survival (PFS)
- 4. Incidence of Richter's transformation

4.2.3 EXPLORATORY ENDPOINTS

- 1. Alterations of T-cell function: We postulate that there will be increased polarization towards TH1 compartment cells, which will be associated with increased cellular immunity. PD-1 blockage will increase TH1 mediated anti-tumor response.
- 2. Alterations in B-cell function: Combination of BTK and PD-1 inhibition will restore B-cell function
- 3. Alterations in cytokine profile (as defined in Section 4.2.2.2)
- 4. Evaluation of toxicity and safety of the combined therapy: In order to minimize toxicity, pembrolizumab will start 6 weeks prior to ibrutinib

5 STUDY ENROLLMENT AND WITHDRAWAL

5.1 PARTICIPANT INCLUSION CRITERIA

Patients must meet all of the following criteria to be eligible for study entry:

- 1. Have high risk CLL which includes one or more of the following characteristics:
 - a. 17p deletion by FISH or TP53 by NGS.
 - b. 11q deletion or ATM mutation by NGS.
 - c. IgVH unmutated or IgVH mutated 3.21 phenotype by NGS assay
- 2. Have documented previously untreated CLL according to IWCLL criteria.
 - a. Monoclonal B cells that are clonally co-expressing at least 1 B-cell marker on flow cytometry:
 - 1) CD19
 - 2) CD20
 - 3) CD5
 - b. Prolymphocytes may comprise no more than 55% of blood lymphocytes
- 3. Be willing and able to provide written informed consent/assent for the trial.

4. Be greater than 18 years of age on day of signing informed consent.
5. Have a performance status of 0 or 1 on the ECOG Performance Scale.
6. Demonstrate adequate organ function as defined in Table 1.

System	Laboratory Value
Hematological	
Absolute neutrophil count (ANC)	$\geq 1,500 / \text{mcL}$
Platelets	$\geq 100,000 / \text{mcL}$
Hemoglobin	$\geq 11 \text{ g/dL}$
Renal	
Serum creatinine OR Measured or calculated ^a creatinine clearance (GFR can also be used in place of creatinine or CrCl)	$\leq 1.5 \times \text{upper limit of normal (ULN)}$ OR $\geq 25 \text{ mL/min}$ for subject with creatinine levels $> 1.5 \times$ institutional ULN
Hepatic	
Serum total bilirubin	$\leq 1.5 \times \text{ULN}$ OR Direct bilirubin $\leq \text{ULN}$ for subjects with total bilirubin levels $> 1.5 \text{ ULN}$
AST (SGOT) and ALT (SGPT)	$\leq 2.5 \times \text{ULN}$
Coagulation	
International Normalized Ratio (INR) or Prothrombin Time (PT)	$\leq 1.5 \times \text{ULN}$ unless subject is receiving anticoagulant therapy as long as PT or PTT is within therapeutic range of intended use of anticoagulants
Activated Partial Thromboplastin Time (aPTT)	$\leq 1.5 \times \text{ULN}$ unless subject is receiving anticoagulant therapy as long as PT or PTT is within therapeutic range of intended use of anticoagulants
^a Creatinine clearance should be calculated per institutional standard.	

7. Negative serum pregnancy test within 3 days prior to receiving the first dose of study medication for a female subject of childbearing potential. Subjects of childbearing potential are those who have not been surgically sterilized or have not been free from menses for > 1 year. Women who are pregnant or breastfeeding are ineligible for this study.
8. Female subjects of childbearing potential must be willing to use 2 methods of highly effective contraception, be surgically sterile, or abstain from heterosexual activity for the course of the study through 30 days and 90 days after the last dose of study medication for ibrutinib and pembrolizumab, respectively (Reference Section 5.7.2). Male subjects must agree to use an adequate method of contraception starting with the first dose of study therapy through 90 days after the last dose of study therapy. Men must agree to not donate sperm during and after the study.
9. Is able to take oral medication and is willing to adhere to the medication regimen.

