- **Infusion-related reactions:** Acute infusion reactions (which can include cytokine release syndrome, angioedema, or anaphylaxis) are different from allergic/hypersensitive reactions, although some of the manifestations are common to both AEs. Signs and symptoms usually develop during or shortly after drug infusion and generally resolve completely within 24 hours of completion of infusion. Signs/symptoms may include: Allergic reaction/hypersensitivity (including drug fever); Arthralgia (joint pain); Bronchospasm; Cough; Dizziness; Dyspnea (shortness of breath); Fatigue (asthenia, lethargy, malaise); Headache; Hypertension; Hypotension; Myalgia (muscle pain); Nausea; Pruritis/itching; Rash/desquamation; Rigors/chills; Sweating (diaphoresis); Tachycardia; Tumor pain (onset or exacerbation of tumor pain due to treatment); Urticaria (hives, welts, wheals); Vomiting. Pembrolizumab can cause severe or life-threatening infusion-related reactions and has been reported in 6 (0.2%) out of 2799 patients that received the drug.
- **Embryo-fetal toxicity:** Based on its mechanism of action, pembrolizumab can cause fetal harm when administered to a pregnant woman. Animal models link the PD-1/PD-L1 signaling pathway with maintenance of pregnancy through induction of maternal immune tolerance to fetal tissue. If this drug is used during pregnancy, or if the patient becomes pregnant while taking this drug, apprise the patient of the potential hazard to a fetus. Advise females of reproductive potential to use highly effective contraception during treatment with pembrolizumab and for 4 months after the last dose of the drug.

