4 STUDY DESIGN AND ENDPOINTS

4.1 DESCRIPTION OF THE STUDY DESIGN

Trial Design

The trial is an open-label, single arm phase II study to be conducted only at the Moffitt Cancer Center. Anticipated accrual will be 25 subjects. One of the secondary endpoint of this study is reconstitution of immune function, using response to pneumococcal vaccination as a clinical surrogate representation of global immune function. The study is designed to test the null hypothesis that, in high risk CLL (defined as presence of del17p or TP53, del11q or ATM mutation, unmutated IGVH or mutated IGVH with 3.21 phenotype) patients who do not require treatment of CLL and receive PD-1:PD-L1 blockade along with ibrutinib, challenge with the 7-valent pneumococcal vaccine will elicit an immunologic response <40%, defined as the generation of detectable antibody responses to >6 antigens. Our specified alternative hypothesis is that vaccination in the context of PD-1 blockade and ibrutinib will elicit an immunologic response >60% with 90% power.

Overall treatment Schema: All intravenous treatments will be administered at the outpatient Moffitt Cancer Center Infusion Center. The patients will receive a combination of IV pembrolizumab (anti-PD1) and oral ibrutinib according to the scheduled depicted in Figure 1. Briefly, patients will receive pembrolizumab on a 3-week interval schedule for a total of at least 51 weeks (it could be extended for up to 2 years if clinical benefit per investigator); starting with week 6, patients will additionally start daily oral ibrutinib which will be continued through 54 weeks of ibrutinib therapy. The rationale of starting pembrolizumab first is to avoid overlapping toxicity of ibrutinib and the anti-PD1 antibody.

Biomarker Research

Immune Monitoring Laboratory Correlates:

1. Global Immune function will be assessed in terms of serum cytokine patterns. Patient sera will be evaluated by flow cytometric means using cytokine bead arrays to measure serum cytokine levels quantitatively. The cytokine panel will include IFN- γ , TNF- α , IL-2, IL-4, IL-10, IL-6, IL-17A, allowing discrimination between TH1, TH2, and TH17 profiles.

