5.2 PARTICIPANT EXCLUSION CRITERIA

Any of the following is a criterion for exclusion from the study:

1. Is currently participating in or has participated in a study of an investigational agent or using an investigational device within 4 weeks of the first dose of treatment.
2. Has had any treatment for CLL including any investigational agent, chemotherapy, mAb, anti-PD-1, anti-PDL-1, or anti-CTLA-4.
3. Meets iwCLL criteria to start therapy (Appendix A).

4. Transformation of CLL to aggressive NHL (Richter's transformation or pro-lymphocytic leukemia)
5. Known active central nervous system (CNS) metastases and/or carcinomatous meningitis.
6. Has an active autoimmune disease requiring systemic treatment within the past 3 months or a documented history of clinically severe autoimmune disease, or a syndrome that requires systemic steroids or immunosuppressive agents including subjects with uncontrolled autoimmune hemolytic anemia or immune thrombocytopenia. Subjects with vitiligo or resolved childhood asthma/atopy would be an exception. Subjects that require intermittent use of bronchodilators or local steroid injections would not be excluded from the study. Subjects with hypothyroidism stable on hormone replacement or Sjorgen's syndrome will not be excluded from the study.
7. Has history of (non-infectious) pneumonitis that required steroids or current pneumonitis.
8. Has an active infection requiring systemic therapy.
9. Has a history or current evidence of any condition, therapy, or laboratory abnormality that might confound the results of the trial, interfere with the subject's participation for the full duration of the trial, or is not in the best interest of the subject to participate, in the opinion of the treating investigator.
10. Subjects with a history of a different malignancy are ineligible unless they have been disease free for 1 year and considered low risk for relapse, except for: cervical cancer in situ, ductal carcinoma in situ, localized prostate cancer with no detectable disease by imaging studies, and non-melanoma skin cancers which are eligible at any time.
11. Has known psychiatric or substance abuse disorders that would interfere with cooperation with the requirements of the trial.
12. Is pregnant or breastfeeding, or expecting to conceive or father children within the projected duration of the trial, starting with the pre-screening or screening visit through 90 days after the last dose of trial treatment.

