5.5 PREMATURE TERMINATION OR SUSPENSION OF STUDY

This study may be temporarily suspended or prematurely terminated if there is sufficient reasonable cause. Written notification, documenting the reason for study suspension or termination, will be provided by the suspending or terminating party to investigator, funding agency, the IND/IDE sponsor and regulatory authorities. If the study is prematurely terminated or suspended, the PI will promptly inform the IRB and will provide the reason(s) for the termination or suspension.

Circumstances that may warrant termination or suspension include, but are not limited to:

1. Quality or quantity of data recording is inaccurate or incomplete
2. Poor adherence to protocol and regulatory requirements
3. Incidence or severity of adverse drug reaction in this or other studies indicates a potential health hazard to subjects
4. Plans to modify or discontinue the development of the study drug
5. Determination of futility

In the event Merck or Janssen decide to no longer supply study drug, ample notification will be provided so that appropriate adjustments to subject treatment can be made.

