6.1.9 DURATION OF THERAPY

The duration of ibrutinib therapy will be up to 51 weeks.

The duration of therapy of pembrolizumab will be up to 51 weeks. Pembrolizumab dosing could be extended for up to 2 years if clinical benefit per investigator.

Patients will be considered evaluable if they complete at least 9 weeks or three infusions of pembrolizumab.

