² Pembrolizumab infusions will be every 3 weeks (+/- 3 days) for 51 weeks. Ibrutinib will be dispensed every 3 weeks on the day of the pembrolizumab infusion. The last dispensing of ibrutinib will occur at week 51 and dosing will continue for an additional 3 weeks. A pill diary will be provided to participants with every dispensing of ibrutinib supply. Pill diary from previous dispensing will be reviewed for accountability.

³ Serum pregnancy test will be performed on females of childbearing potential (FCBP). A FCBP is considered when a sexually mature female: 1) has not undergone a hysterectomy or bilateral oophorectomy; or 2) has not been naturally postmenopausal for at least 12 consecutive months.

⁴ Hematology will consist of CBC and differential with platelet counts. CBC/differential will be performed at day 1, week 0,1,2 after starting pembrolizumab and then weekly for the first month on ibrutinib (weeks 6, 7, 8, 9, 10). Starting at week 12, CBC/diff will be performed on days of the clinic visits for physical examinations/drug administration. Further CBCs with differential will be performed per physician discretion.

⁵ CMP includes: sodium, potassium, chloride, CO2, calcium, BUN, creatinine, glucose, albumin, total protein, alkaline phosphatase, total bilirubin, AST/SGOT, ALT/SGPT, LDH. Subjects will have CMP , week 0, 1, 2 after starting pembrolizumab and then weekly for the first month on ibrutinib (weeks 6, 7, 8, 9, 10). Starting at week 12, CMP will be performed on days of the clinic visits for physical examinations/drug administration. Further CMPs will be performed per investigator discretion.

⁶ TLS (tumor lysis syndrome) laboratory assessment will include: BUN, creatinine, phosphorus, potassium, LDH, uric acid. TLS laboratory evaluation will occur at days 1-3 of week 0 weeks 1 and 2 after starting pembrolizumab and then weekly for the first month on ibrutinib (weeks 6, 7, 8, 9, 10). Further TLS assessments will depend on clinical condition and/or at investigator discretion.

⁷ Peripheral blood samples for ZAP-70, IgVH mutational status, and FISH testing will be done ONLY if not ever performed. Previous results must be available in the medical record for determination of eligibility.

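### Inclusion criterion 8 ends required female contraception 90 days after pembrolizumab, about a month short of the 4 months advised in Section 2.3.1

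*Combined protocol and SAP*

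**What the plan says.** Section 5.1, criterion 8, makes entry for women of childbearing potential conditional on willingness to use two highly effective methods, or on surgical sterility or abstinence. The obligation runs "through 30 days and 90 days after the last dose of study medication for ibrutinib and pembrolizumab, respectively". The criterion refers the reader to Section 5.7.2.

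Section 2.3.1, in the pembrolizumab paragraph on embryo-fetal toxicity, says that females of reproductive potential should be advised to "use highly effective contraception during treatment with pembrolizumab and for 4 months after the last dose of the drug". The ibrutinib paragraph of that section gives 1 month after stopping, which agrees with the 30 days in criterion 8.

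Section 5.2, exclusion 12, bars people who expect to conceive or father a child in a period "starting with the pre-screening or screening visit through 90 days after the last dose of trial treatment".

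The relative timing of the two last doses matters, and the protocol gives several versions:

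- Section 7.3.7, footnote 2: "The last dispensing of ibrutinib will occur at week 51 and dosing will continue for an additional 3 weeks". Ibrutinib therefore ends at week 54; Section 5.4.1 says the same.
- Section 6.1.9: "The duration of ibrutinib therapy will be up to 51 weeks". Counted from the week-6 start, that is week 57.
- Section 4.1: ibrutinib, "which will be continued through 54 weeks of ibrutinib therapy". Counted from week 6, that is week 60.
- Section 6.1.9 also says: "Pembrolizumab dosing could be extended for up to 2 years if clinical benefit per investigator". Pembrolizumab may therefore be the last drug given.

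**The concern.** The two periods concern the same drug and the same women, and both count from the last pembrolizumab dose, yet they differ by about a month. The shorter one is the condition of entry. The longer one sits in a background section on risks, and no eligibility or conduct text in the available document carries it forward. A woman who meets criterion 8 exactly can stop contraception while she is still within the period for which the protocol warns of fetal risk.

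The cross-reference that might have settled the matter leads nowhere: the last subsection of Section 5 is 5.5, "PREMATURE TERMINATION OR SUSPENSION OF STUDY", and Section 6 follows.

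What is at stake is avoidable fetal exposure. It is unlikely in this population but serious if it happens. The trial's statistical conclusions are not at stake.

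**Working it through.** **Inputs**

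- Required period after the last pembrolizumab dose: 90 days (criterion 8).
- Required period after the last ibrutinib dose: 30 days (criterion 8).
- Advised period after the last pembrolizumab dose: 4 months (Section 2.3.1).
- Bar on planned conception: 90 days after the last dose of trial treatment (exclusion 12).
- Last scheduled pembrolizumab infusion: taken as week 51, unless pembrolizumab is extended and ends last.
- Last ibrutinib dose: week 54, 57 or 60, according to the section read.

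**Step 1: length of 4 months.** Over all calendar start dates, four months last 120 to 123 days. The basic shortfall is 120 − 90 = 30 to 123 − 90 = 33 days.

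**Step 2: does the ibrutinib clause extend the obligation?** Let *lag* be the days from the last pembrolizumab dose to the last ibrutinib dose, set to 0 when pembrolizumab ends last. Counting from the last pembrolizumab dose:

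- Criterion 8 ends on day max(90, lag + 30).
- Exclusion 12 ends on day lag + 90.
- Shortfall of criterion 8 = (120 to 123) − its end day.
- Days outside both rules = (120 to 123) − the later of the two end days, or 0 if negative.

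| Last dose | Lag | Lag + 30 | Criterion 8 ends | Shortfall | Exclusion 12 ends | Outside both |
|---|---|---|---|---|---|---|
| Pembrolizumab last | 0 | 30 | day 90 | 30–33 | day 90 | 30–33 |
| Ibrutinib, week 54 | 3 × 7 = 21 | 51 | day 90 | 30–33 | day 111 | 9–12 |
| Ibrutinib, week 57 | 6 × 7 = 42 | 72 | day 90 | 30–33 | day 132 | 0 |
| Ibrutinib, week 60 | 9 × 7 = 63 | 93 | day 93 | 27–30 | day 153 | 0 |

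The last two columns show only how far exclusion 12 overlaps the advised period. That criterion concerns intended conception. It requires no contraception and does not address unplanned pregnancy, so it does not reduce the shortfall in criterion 8.

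**Step 3: when does the gap close?** It closes when lag + 30 reaches 120 to 123, that is, lag of at least 90 to 93 days, or 12.9 to 13.3 weeks. This needs ibrutinib to continue about 13 weeks past pembrolizumab, for example after pembrolizumab is stopped early.

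**Step 4: how many women?** The documents give no number of women of childbearing potential. If the sex ratio of the team's earlier frontline trial (15 women of 45, Section 5.3) carries over, 25 × 15/45 = 8.3 women of any age are expected. With a median age at diagnosis of 67 to 72, those of childbearing potential will be fewer and could be none.

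**The case against.** The strongest reply is that the texts do not contradict each other. Section 2.3.1 is counselling advice in a risk summary; criterion 8 is a statement of willingness at entry. A woman can satisfy both, and a shorter entry minimum does not withdraw the longer advice. Criterion 8 is also stricter in one respect, since it asks for two methods. That both can be followed is true. Even so, a stated minimum below the protocol's own fetal-risk advice is a defect: the minimum is what a participant agrees to, and asking for two methods does not lengthen the period.

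A second reply is that 90 days is a window used throughout the trial: for male contraception, exclusion 12, pregnancy reporting (Section 8.1.1.2) and safety reporting. That probably explains the figure, but it does not show that 90 days meets the 4-month advice.

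Third, criterion 8 opens by covering the course of the study, which might be read to include follow-up. The same sentence sets its end points at 30 and 90 days after the last doses, and the wider reading would leave those limits without meaning.

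Three further points stand. The consent pages are not available, so what women were actually told is unknown; they may have been told 4 months. The week-57 and week-60 cases come from separate inconsistencies about ibrutinib duration and change the answer little. The number affected is very small. These points limit the weight of the finding but do not reconcile criterion 8 with Section 2.3.1.

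**Conclusion.** The concern holds, as a minor internal inconsistency in a safety requirement. Criterion 8 falls short of the 4 months advised in Section 2.3.1 by 30 to 33 days if pembrolizumab ends last or ibrutinib ends at week 54 or 57, by 27 to 30 days if ibrutinib ends at week 60, and by nothing if ibrutinib outlasts pembrolizumab by about 13 weeks or more.

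This rests on reading 4 months as calendar months, on a week-51 last infusion unless pembrolizumab ends last, and on criterion 8 running to the later of its two end dates, which its wording does not state outright. The ibrutinib periods agree and need no change. No statistical quantity in the plan is affected.

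**What to change.** In criterion 8, replace the female post-pembrolizumab period of 90 days with 4 months, keep 30 days for ibrutinib, and say which date governs. Suggested wording: *through the later of 30 days after the last ibrutinib dose and 4 months (at least 120 days) after the last pembrolizumab dose*. Remove or correct the reference to Section 5.7.2. If the consent form repeats 90 days, change it too.

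The windows in exclusion 12 and in pregnancy reporting (Section 8.1.1.2) set no contraception period. Aligning them with 4 months would be tidy, but the correction does not depend on it.

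The cost is a wording amendment to one criterion, possibly a consent revision, and about one extra month of contraception for few participants. The statistical design is unchanged.

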5.2 PARTICIPANT EXCLUSION CRITERIA

Any of the following is a criterion for exclusion from the study:

1. Is currently participating in or has participated in a study of an investigational agent or using an investigational device within 4 weeks of the first dose of treatment.
2. Has had any treatment for CLL including any investigational agent, chemotherapy, mAb, anti-PD-1, anti-PDL-1, or anti-CTLA-4.
3. Meets iwCLL criteria to start therapy (Appendix A).

4. Transformation of CLL to aggressive NHL (Richter's transformation or pro-lymphocytic leukemia)
5. Known active central nervous system (CNS) metastases and/or carcinomatous meningitis.
6. Has an active autoimmune disease requiring systemic treatment within the past 3 months or a documented history of clinically severe autoimmune disease, or a syndrome that requires systemic steroids or immunosuppressive agents including subjects with uncontrolled autoimmune hemolytic anemia or immune thrombocytopenia. Subjects with vitiligo or resolved childhood asthma/atopy would be an exception. Subjects that require intermittent use of bronchodilators or local steroid injections would not be excluded from the study. Subjects with hypothyroidism stable on hormone replacement or Sjorgen's syndrome will not be excluded from the study.
7. Has history of (non-infectious) pneumonitis that required steroids or current pneumonitis.
8. Has an active infection requiring systemic therapy.
9. Has a history or current evidence of any condition, therapy, or laboratory abnormality that might confound the results of the trial, interfere with the subject's participation for the full duration of the trial, or is not in the best interest of the subject to participate, in the opinion of the treating investigator.
10. Subjects with a history of a different malignancy are ineligible unless they have been disease free for 1 year and considered low risk for relapse, except for: cervical cancer in situ, ductal carcinoma in situ, localized prostate cancer with no detectable disease by imaging studies, and non-melanoma skin cancers which are eligible at any time.
11. Has known psychiatric or substance abuse disorders that would interfere with cooperation with the requirements of the trial.
12. Is pregnant or breastfeeding, or expecting to conceive or father children within the projected duration of the trial, starting with the pre-screening or screening visit through 90 days after the last dose of trial treatment.
13. Has a known history of Human Immunodeficiency Virus (HIV) (HIV 1/2 antibodies).
14. Has known active Hepatitis B (e.g., HBsAg reactive) or Hepatitis C (e.g., HCV RNA [qualitative] is detected).
15. Has received a live vaccine within 30 days prior to the first dose of trial treatment. Patients who had pneumococcal vaccination within 6 months from starting trial will not be eligible for the study.
16. Major surgery or a wound that has not fully healed within 4 weeks of first dose.
17. History of stroke or intracranial hemorrhage within 6 months prior to first dose.
18. Requires anticoagulation with warfarin or equivalent vitamin K antagonists (eg, phenprocoumon).
19. Requires chronic treatment with strong CYP3A inhibitors.
20. Clinically significant cardiovascular disease such as uncontrolled or symptomatic arrhythmias, congestive heart failure, or myocardial infarction within 6 months of Screening, or any Class 3 (moderate) or Class 4 (severe) cardiac disease as defined by the New York Heart Association Functional Classification.

